8.8. Exposure During Pregnancy

An exposure during pregnancy (also referred to as exposure in-utero [EIU]) occurs if:

1. A female becomes, or is found to be, pregnant either while receiving or having been directly exposed to (eg, environmental exposure) maraviroc, or the female becomes, or is found to be, pregnant after discontinuing and/or being directly exposed to maraviroc (maternal exposure);
2. A male has been exposed, either due to treatment or environmental, to maraviroc prior to or around the time of conception and/or is exposed during his partner's pregnancy (paternal exposure).

If any study subject or study subject's partner becomes or is found to be pregnant during the study subject's treatment with maraviroc, the investigator must submit this information to Pfizer, as the Sponsor's designated representative, within 24 hours of awareness of pregnancy, irrespective of whether an adverse event has occurred.

Follow-up is conducted to obtain pregnancy outcome information on all Exposure in Utero reports with an unknown outcome. The investigator will follow the pregnancy until completion or until pregnancy termination (eg, induced abortion) and then notify Pfizer, as the Sponsor's designated representative, of the outcome. The investigator will provide this information as a follow up to the initial Exposure in Utero Form.

8.8.1. Medication Error

A medication error is any preventable event that may cause or lead to inappropriate medication use or patient harm while the medication is in the control of the health care professional, patient, or consumer. Such events may be related to professional practice, health care products, procedures, and systems including: prescribing; order communication; product labeling, packaging, and nomenclature; compounding; dispensing; distribution; administration; education; monitoring; and use.

Medication errors include:

- near misses, involving or not involving a patient directly (eg, inadvertent/erroneous administration, which is the accidental use of a product outside of labeling or prescription on the part of the healthcare provider or the patient/consumer).
- confusion with regard to invented name (eg, trade name, brand name).

The investigator must submit the following medication errors to Pfizer within 24 hours of awareness, irrespective of whether an adverse event occurred:

- Medication errors involving patient exposure to the product, whether or not the medication error is accompanied by an AE.
- Medication errors including potential medication errors or near misses that do not involve a patient directly. When a medication error does not involve patient exposure to the product the following minimum criteria constitute a medication error report:
 - An identifiable reporter;
 - A suspect product;
 - A medication error including potential medication error or near miss.

8.9. Reporting Requirements

Each adverse event is to be assessed to determine if it meets the criteria for serious adverse event. If a serious adverse event occurs, expedited reporting will follow local and international regulations, as appropriate.

8.9.1. Serious Adverse Event Reporting Requirements

If a serious adverse event occurs, Pfizer is to be notified within 24 hours of awareness of the event by the investigator. In particular, if the serious adverse event is fatal or life-threatening, notification to Pfizer must be made immediately, irrespective of the extent of available adverse event information. This timeframe also applies to additional new information (follow-up) on previously forwarded serious adverse event reports as well as to the initial and follow-up reporting of exposure during pregnancy cases.

In the rare event that the investigator does not become aware of the occurrence of a serious adverse event immediately (eg, if an outpatient study subject initially seeks treatment elsewhere), the investigator is to report the event within 24 hours after learning of it and document the time of his/her first awareness of the adverse event.

For all serious adverse events, the investigator is obligated to pursue and provide information to Pfizer in accordance with the timeframes for reporting specified above. In addition, an investigator may be requested by Pfizer to obtain specific additional follow-up information in an expedited fashion. This information collected for serious adverse events is more detailed than that captured on the adverse event case report form. In general, this will include a description of the adverse event in sufficient detail to allow for a complete medical assessment of the case and independent determination of possible causality. Information on other possible causes of the event, such as concomitant medications and illnesses must be provided. In the case of a subject death, a summary of available autopsy findings must be submitted as soon as possible to the Sponsor or its designated representative.

8.9.2. Non-serious Adverse Event Reporting Requirement

Non-serious adverse events are to be reported if they are suspected to be related to maraviroc (ie, adverse reaction) on the adverse event page, which is to be submitted to Pfizer, as the Sponsor's designated representative.

8.10. Communication of Issues

In the event of any prohibition or restriction imposed (eg, clinical hold) by an applicable Competent Authority in any area of the World, or if the investigator is aware of any new information which might influence the evaluation of the benefits and risks of maraviroc, Pfizer, as the Sponsor's designated representative, should be informed immediately.

In addition, the investigator will inform Pfizer, as the Sponsor's designated representative, immediately of any urgent safety measures taken by the investigator to protect the study subjects against any immediate hazard, and of any serious breaches of this non-interventional study protocol that the investigator becomes aware of.

9. DATA ANALYSIS/STATISTICAL METHODS

Detailed methodology for summary and statistical analyses of data collected in this study will be documented in a Statistical Analysis Plan, which will be dated, filed, and maintained by the sponsor. This document may modify the plans outlined in the protocol; however, any major modifications of the primary endpoint definition and/or its analysis will also be reflected in a protocol amendment.

9.1. Sample Size

The sample size for the study was determined based on an extensive feasibility assessment in 28 countries, input from Pfizer country offices, and in consultation with the regulators. This number was estimated to be 3,000 subjects (1,500 patients receiving maraviroc and

1,500 patients not receiving maraviroc) to allow calculations of reliable and precise risk estimates.

Malignancies, myocardial ischemia or infarction and deaths (liver-related and all cause) occurring at any time during the 5-year follow-up period will be adjudicated and analyzed as study endpoints. Assuming up to 10% annual loss to follow-up, the 1,500 patients each receiving maraviroc or the anchor drug will contribute 5,836 person-years of observation for these study endpoints over a 5-year period (See Scenario 1 in [Appendix 3](#) for details) in each treatment arm. It is assumed that the expected incidence rates are 12.7 per 1000 person-years for malignancies,¹⁴ 3.5 per 1,000 person-years for myocardial infarction,¹³ 2.35 per 1,000 person-years for liver-related deaths,¹⁵ and 16 per 1,000 person-years for all cause mortality¹⁵ in the internal comparator group of patients not receiving maraviroc.

CDC category C AIDS-defining opportunistic infections, viral encephalitis, rhabdomyolysis and liver failure will be adjudicated and analyzed as study endpoints if they occur during the use of maraviroc or the anchor drug in the OBT arm or within 6 months following maraviroc or anchor drug discontinuation. Accounting for the expected rates of drug discontinuation in the two treatment arms over time and a 10% annual loss to follow-up, each study arm will accrue 2,875 person-years of observation for these study endpoints (See Scenario 2 in [Appendix 3](#) for details). It is assumed that the expected incidence rates are 3.5 per 1,000 person-years for liver failure,¹⁶ and 160 per 1,000 person-years for AIDS-defining opportunistic infections¹⁷ in the internal comparator group of patients not receiving maraviroc.

Based on these assumptions of equal person years of contribution in the maraviroc exposed and unexposed groups, using a two-tailed test with $\alpha=0.05$, and a power of 80%, the minimum detectable relative rates for various study end points are reported in Table 2.¹⁸

Table 2. Minimum detectable relative rates using a two sided test, $\alpha =0.05$, and a power of 80%

End Point	Expected number of events in the unexposed internal comparator group	Detectable Relative rates
Malignancies	74	1.572
AIDS-defining opportunistic infections	460	1.1955
Myocardial infarction	20	2.136
Liver failure	10	2.760
Liver-related deaths	14	2.410
All cause mortality	93	1.464

For example, results from Table 2 suggest that the study has 80% power to detect a relative risk of ≥ 1.527 for malignancies and ≥ 1.196 for AIDS-defining opportunistic infections, respectively for the patients receiving maraviroc. Similar conclusions can be drawn for other end points as well.

09017e1928d33f51Approved/Approved On: 07-Jan-2020 12:23 (GMT)

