Based on these assumptions of equal person years of contribution in the maraviroc exposed and unexposed groups, using a two-tailed test with  $\alpha=0.05$ , and a power of 80%, the minimum detectable relative rates for various study end points are reported in Table 2. (McMahon, A.D. and T.M. MacDonald, 1997).

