6. Crude and adjusted rate ratios with 95% confidence intervals will be calculated for each study endpoint comparing maraviroc-exposed patients to maraviroc-unexposed patients. Multivariate analysis techniques will be used as appropriate (e.g., Poisson regression model) to account for the baseline difference in the two study groups via propensity score technique. Specifically, since subjects are not randomized to treatment, there is a potential for imbalance in the above-mentioned important demographic and baseline characteristics between groups. To account for the imbalance between the two groups on the clinically important demographic and baseline characteristics, the confidence intervals will be adjusted for propensity score quintile. Specifically, propensity score for treatment membership (maraviroc exposed vs. maraviroc un-exposed) will be calculated for each subject from a logistic regression with the above mentioned covariates as predictors and study group membership as the outcome. Participants with similar propensity scores generally have similar distribution of the covariates on which the score is based. Participants will then be categorized into quintiles according to their propensity score. Four indicator variables will be created to represent the propensity score quintiles and will be used in the multivariate model as covariates along with the primary exposure variable i.e., exposure to maraviroc. Adjusting for propensity score quintile in this manner helps account for imbalances at baseline as discussed in D'Agostino (1998).
7. Appropriate survival analyses techniques (eg, Kaplan-Meier survival curves, Cox proportional hazards model) will be used to further analyze the data. The multivariate models will incorporate appropriate techniques referred to in section 4.2.3 to adjust for

potential survival bias.

8. In addition, incidence rates in patients receiving maraviroc in this study may be compared to those reported in comparable patients (ie, those with similar propensity scores and with the smallest Mahalanobis' distance between baseline values (D'Agostino, 1998) not using maraviroc in other HIV-1 infected cohort(s) such as EuroSIDA. The baseline characteristics of the patients (eg, number of failed regimens, CD4+ T lymphocyte counts) in this study will be used to identify comparable subjects from the external cohort(s).

The following data will be presented in standard safety summaries:

- *adverse events*

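### Table 2 and its 80% power statement describe the unadjusted rate ratio; that power is not established for the propensity-quintile-adjusted ratio the SAP uses to control confounding

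*Protocol*

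**What the plan says.** Protocol 9.1 and SAP 4.2.1 multiply assumed comparator rates by expected person-years to get comparator event counts. They then give the smallest relative rate detectable with a two-sided 5% test and 80% power. The SAP introduces the calculation with "Based on these assumptions of equal person years of contribution in the maraviroc exposed and unexposed groups". No covariate, overlap or variance-inflation term appears among the inputs. The sentence after Table 2 concludes that "results from Table 2 suggest that the study has 80% power to detect a relative risk of" at least 1.527 for malignancies and 1.196 for opportunistic infections, and says the other endpoints can be read the same way.

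Protocol 9.2 item 6 and SAP 8.2 item 6 plan both crude and adjusted rate ratios with 95% confidence intervals. The SAP notes that treatment is not randomized and that baseline imbalance is possible. Its remedy is a model such as Poisson regression with exposure and propensity-score quintile: "Four indicator variables will be created to represent the propensity score quintiles and will be used in the multivariate model as covariates". Neither ratio is named primary, and SAP 4.1 lists no statistical hypotheses.

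**The concern.** The power statement belongs to one estimator, and the estimate that controls confounding is another. Once exposure is associated with propensity quintile, the adjusted log rate ratio draws only on within-quintile contrasts. At the same event totals its variance is then larger than the crude variance behind Table 2.

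This is a post-approval safety commitment to two regulators. If an adjusted ratio for malignancy, MI, liver events or death turns out null, a reader may go to the 80% statement to judge how large a harm the study could have missed. As written, nothing tells that reader that the statement was derived for the unadjusted ratio.

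**Working it through.** **Inputs.** Table 2 gives the comparator events E0 and the ratios. The events follow from the stated rates and from 5,836 person-years (5-year endpoints) or 2,875 (on-drug endpoints). For example, 12.7 × 5.836 = 74.1 malignancies, 160 × 2.875 = 460 opportunistic infections and 3.5 × 5.836 = 20.4 MIs. Allocation is 1:1 with equal person-time, and alpha is 0.05 two-sided. Propensity overlap is not in the documents and is assumed below.

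**Step 1: reproduce Table 2 as a crude comparison.** With E1 = RR × E0, the information on the log rate ratio is I = E0·E1/(E0+E1), and power = Φ(ln RR × √I − 1.960). For malignancies at the text's 1.527:

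- E1 = 74 × 1.527 = 113.0
- I = 74 × 113.0/187.0 = 44.72
- ln 1.527 × √44.72 = 0.4233 × 6.687 = 2.831
- power = Φ(0.871) = 80.8%

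The crude column in Step 3 has the other endpoints. All lie within 2 points of 80%, so Table 2 is an unadjusted calculation. The table's own malignancy entry, 1.572, gives 86.0%; the ratio for exactly 80% is 1.521. Only the text's 1.527 fits.

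**Step 2: put in the quintile model.** With quintile indicators, information becomes the sum over quintiles of a·b/(a+b), where a and b are unexposed and exposed events. That sum never exceeds the pooled value and equals it only if the event split is the same in every quintile. As an example, take a binormal score unrelated to risk with c=0.70, for malignancies at 1.527:

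| Quintile | Unexposed share | Exposed share | a | b | ab/(a+b) |
|---|---|---|---|---|---|
| 1 | 0.298 | 0.102 | 22.1 | 11.5 | 7.57 |
| 2 | 0.241 | 0.159 | 17.8 | 18.0 | 8.95 |
| 3 | 0.200 | 0.200 | 14.8 | 22.6 | 8.94 |
| 4 | 0.159 | 0.241 | 11.8 | 27.2 | 8.22 |
| 5 | 0.102 | 0.298 | 7.5 | 33.7 | 6.17 |

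The sum is about 39.8. Variance inflation is 44.72/39.8 = 1.12, and power = Φ(0.4233 × √39.8 − 1.960) = Φ(0.711) = 76.1%.

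**Step 3: all endpoints, score unrelated to risk, Table 2 event totals.**

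| Endpoint (ratio) | Crude | c=0.60 | c=0.70 | c=0.80 |
|---|---|---|---|---|
| Malignancies (1.527) | 80.8% | 79.7% | 76.1% | 68.7% |
| Opportunistic infections (1.1955) | 80.7% | 79.6% | 75.9% | 68.3% |
| MI (2.136) | 80.0% | 79.0% | 75.7% | 68.6% |
| Liver failure (2.760) | 78.5% | 77.6% | 74.5% | 67.8% |
| Liver-related death (2.410) | 79.0% | 78.1% | 74.8% | 67.9% |
| All-cause death (1.464) | 80.9% | 79.8% | 76.2% | 68.7% |

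Variance inflation is about 1.02–1.03, 1.10–1.13 and 1.29–1.35 in the three adjusted columns. Simulating the Poisson model with quintile indicators for malignancies at 1.527 (2,000 runs) gave 77.2% adjusted against 82.6% crude at c=0.70. At c=0.80 it gave 67.6% against 80.8%, a 13-point gap.

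**Step 4: let the score predict risk.** Assume log risk changes by 0.5 per SD of the score and hold comparator events at Table 2's values. The exposed total is then multiplied by exp(±0.5d), with d = √2·Φ⁻¹(c). At c=0.70, d = 0.742, so the 113 exposed malignancies become 163.7 or 78.0.

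| Adjusted power at c=0.70 | Maraviroc patients at lower baseline risk | At higher baseline risk |
|---|---|---|
| Malignancies (1.527) | 69.2% | 81.8% |
| Opportunistic infections | 68.1% | 82.2% |
| MI | 69.8% | 80.4% |
| Liver failure | 69.4% | 78.6% |
| Liver-related death | 69.3% | 79.3% |
| All-cause death | 69.1% | 81.9% |

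With MI's unrounded 20.4 events, the 69.8% becomes about 71%, because the test statistic scales by √(20.4/20). The ranges are therefore about 68–71% and 78–82%.

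**The case against.** The strongest reply is that the direction is not guaranteed. Table 2 fixes only the comparator events. If maraviroc patients carry higher baseline risk, they have more events and adjusted power can stay at or above the stated level, as Step 4 shows. The printed malignancy ratio of 1.572 also keeps 81.9% adjusted power at c=0.70 with a non-prognostic score. This stands: a reader might infer that the statement overstates adjusted power for every endpoint, and the documents do not support that.

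Second, strong propensity separation is not documented. It is tempting to argue that the plan expects it, because the comparator may include dual/mixed or CXCR4-tropic patients while maraviroc is indicated for CCR5-tropic virus. But tropism is not among the covariates named in SAP 6.2, although HIV-1 RNA and CD4+ count are and could carry disease stage into the score. Every subject must be treatment-experienced, under consideration for maraviroc and tropism-tested, which favours overlap. The SAP speaks only of potential imbalance. This stands too, so the c-statistics are assumptions, and at c=0.60 the loss is trivial.

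Third, little hangs formally on the figure. There are no hypotheses and no primary estimate, the sample size rested on feasibility and regulatory consultation, and the reported confidence intervals will show the precision achieved. This limits the point to the stated sensitivity. It does not make an unqualified statement about the study's power correct for an estimator it was not derived for.

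**Conclusion.** The point holds as one about stated precision. Table 2 and its 80% statement describe an unadjusted comparison, and the documents do not establish that power for the quintile-adjusted ratio. At Table 2's event totals and with a score unrelated to risk, the loss is about 1 point at c=0.60, 4 to 5 at c=0.70 and 11 to 13 at c=0.80. If the score is prognostic (assumed slope 0.5 per SD, comparator events fixed), adjusted power at c=0.70 is about 68–71% or 78–82%, depending on which group has the higher baseline risk.

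The c-statistic, the slope and its sign are all assumptions. The crude basis of Table 2, and the rule that stratifying cannot add information at fixed event totals, are not. The malignancy figures are measured against 1.527.

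**What to change.** In Protocol 9.1 and SAP 4.2.1:

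1. Keep the crude calculation, but label Table 2 and the sentence after it as applying to the unadjusted rate ratio.
2. State that the 80% does not carry over to the adjusted ratio of SAP 8.2 item 6.
3. Add a sensitivity column of ratios detectable with 80% power at stated, assumed variance inflation V, labelled as holding event totals at Table 2's basis. Solving ln RR × √(E0·RR/((1+RR)·V)) = 1.960 + 0.842 gives:

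| Endpoint | V=1.0 | V=1.1 | V=1.2 | V=1.3 |
|---|---|---|---|---|
| Malignancies | 1.521 | 1.550 | 1.578 | 1.605 |
| Opportunistic infections | 1.194 | 1.204 | 1.213 | 1.222 |
| MI | 2.136 | 2.208 | 2.278 | 2.347 |
| Liver failure | 2.806 | 2.933 | 3.059 | 3.183 |
| Liver-related death | 2.434 | 2.529 | 2.622 | 2.715 |
| All-cause death | 1.458 | 1.483 | 1.507 | 1.531 |

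4. Reconcile the malignancy ratio, printed as 1.572 in the table and 1.527 in the text.

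The cost is a wording change in two documents and a short recalculation. Enrollment, endpoints and analyses stay as they are. The downside is slightly less favourable stated detectable ratios.

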#### **4.2. Statistical Decision Rules**

##### **4.2.1. Sample Size**

*The sample size for the study was determined based on an extensive feasibility assessment in 28 countries, input from Pfizer country offices, and in consultation with the regulators. This number was estimated to be 3,000 subjects (1,500 patients receiving maraviroc and 1,500 patients not receiving maraviroc) to allow calculations of reliable and precise risk estimates.*

*Malignancies, myocardial ischemia or infarction and deaths (liver-related and all cause) occurring at any time during the 5-year follow-up period will be adjudicated and analyzed as study endpoints. Assuming up to 10% annual loss to follow-up, the 1,500 patients each receiving maraviroc or the anchor drug will contribute 5,836 person-years of observation for these study endpoints over a 5-year period (See Scenario 1 in Appendix 3 for details) in each treatment arm. It is assumed that the expected incidence rates are 12.7 per 1000 person-years for malignancies, (Beral, V. et al, 2000) 5 per 1,000 person-years for myocardial infarction, (Friis-Moller, N, et al, 2003) 2.35 per 1,000 person-years for liver-related deaths, (Weber, R, et al 2006) and 16 per 1,000 person-years for all cause mortality (Weber, R, et al 2006) in the internal comparator group of patients not receiving maraviroc.*

*CDC category C AIDS-defining opportunistic infections, viral encephalitis, rhabdomyolysis and liver failure will be adjudicated and analyzed as study endpoints if they occur during the use of maraviroc or the anchor drug in the OBT arm or within 6 months following maraviroc or anchor drug discontinuation. Accounting for the expected rates of drug discontinuation in the two treatment arms over time and a 10% annual loss to follow-up, each study arm will accrue 2,875 person-years of observation for these study endpoints (See Scenario 2 in Appendix 3 for details). It is assumed that the expected incidence rates are 3.5 per 1,000 person-years for liver failure, (Friis-Moller, N., Kirk O, Reiss P, 2003) and 160 per 1,000 person-years for AIDS-defining opportunistic infections (Kaplan, J.E., et al., 2000) in the internal comparator group of patients not receiving maraviroc.*

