**Table 2. Minimum detectable relative rates using a two sided test,  $\alpha =0.05$ , and a power of 80%**

End Point	Expected number of events in the unexposed internal comparator group	Detectable Relative rates
Malignancies	74	1.572
AIDS-defining opportunistic infections	460	1.1955
Myocardial infarction	20	2.136
Liver failure	10	2.760
Liver-related deaths	14	2.410
All cause mortality	93	1.464

*For example, results from Table 2 suggest that the study has 80% power to detect a relative risk of  $\geq 1.527$  for malignancies and  $\geq 1.196$  for AIDS-defining opportunistic infections, respectively for the patients receiving maraviroc. Similar conclusions can be drawn for other end points as well.*

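### Table 2 prints a detectable malignancy relative rate of 1.572, the sentence reading from it says 1.527, and recomputation supports about 1.53

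*Protocol*

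**What the plan says.** Protocol 9.1 and SAP 4.2.1 give minimum detectable relative rates for six endpoints, for a two-sided 0.05 test with 80% power and equal person-years in the two groups.

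- **Event count.** In the protocol the "expected incidence rates are 12.7 per 1000 person-years for malignancies", and each arm "will contribute 5,836 person-years of observation for these study endpoints over a 5-year period".
- **Table entry.** The malignancy row reads "Malignancies 74 1.572": endpoint, expected comparator events, detectable relative rate.
- **Sentence below the table.** It says that "the study has 80% power to detect a relative risk of ≥ 1.527 for malignancies". It also gives 1.196 for AIDS-defining opportunistic infections, which is the table's 1.1955 rounded.
- **SAP.** Its Table 2 has the same malignancy row, and its sentence ("results from Table 2 suggest that the study has 80% power to detect a relative risk of" and so on) also gives 1.527.

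The protocol and SAP therefore agree with each other. The conflict lies between the table and the sentence inside each document.

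**The concern.** The sentence claims to report the table, so the two malignancy values should be equal. Rounding accounts for the opportunistic infection pair but cannot turn 1.572 into 1.527. The two numbers differ only by an exchange of their last two digits, which suggests a typing slip. The same digits stand in the same places in two separate documents, so a PDF reading fault is an unlikely cause.

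Table 2 is where the plan states what the study can detect. Malignancy is one of the theoretical risks behind the study (protocol 1.2.4.2 and 1.2.5), and the study is a post-approval commitment to regulators. A reader asking how large an excess of malignancy the study could detect gets two answers.

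**Working it through.** **Inputs (protocol 9.1, Table 2):** malignancy rate 12.7 per 1,000 person-years; 5,836 person-years per arm, with loss to follow-up already included; equal person-time; two-sided 0.05; 80% power.

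**Step 1: reproduce the event count.** 12.7/1000 × 5,836 = 74.1, so the printed 74 is right. Using Appendix 3's 5,835 person-years instead gives 74.10 rather than 74.12, which is immaterial.

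**Step 2: choose a formula.** The documents cite a method paper but do not print its formula, so I calibrated one on the table itself. With E comparator events and relative rate R, take T = E(1+R) total events and p = R/(1+R), the probability that an event falls in the exposed group. The continuity-corrected conditional test has 80% power at the R that solves

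T(p − 0.5) − 0.5 = 1.96 × 0.5√T + 0.8416 × √(T p(1 − p)).

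**Step 3: run all six rows at the printed event counts.**

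| Endpoint | E | Printed | Computed | Difference | Power at printed rate |
|---|---|---|---|---|---|
| Opportunistic infections | 460 | 1.1955 | 1.1955 | 0.0000 | 80.0% |
| Myocardial infarction | 20 | 2.136 | 2.1369 | 0.0009 | 79.9% |
| Liver failure | 10 | 2.760 | 2.7574 | 0.0026 | 80.1% |
| Liver-related deaths | 14 | 2.410 | 2.4183 | 0.0083 | 79.6% |
| All-cause mortality | 93 | 1.464 | 1.4643 | 0.0003 | 79.9% |
| Malignancies, table | 74 | 1.572 | 1.5279 | 0.0441 | 85.6% |
| Malignancies, sentence | 74 | 1.527 | 1.5279 | 0.0009 | 79.9% |

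**Step 4: the malignancy power in full.**

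- R = 1.572: T = 74 × 2.572 = 190.3 and p = 0.6112. Then z = (20.664 − 13.520)/6.725 = 1.062, so power is 85.6%.
- R = 1.527: T = 74 × 2.527 = 187.0 and p = 0.6043. Then z = (18.999 − 13.401)/6.687 = 0.837, so power is 79.9%.

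**Step 5: check other methods at E = 74.**

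- Exact conditional test: 80% power at 1.5286; power is 85.4% at 1.572 and 79.8% at 1.527.
- Uncorrected conditional 1.513; Wald 1.517; log rate ratio 1.521.
- Log rate ratio with the null variance used for alpha only: 1.564. With the null variance throughout: 1.585. Neither is 1.572, and both miss other rows badly: myocardial infarction 2.33 and 2.43 against 2.136, liver failure 3.26 and 3.50 against 2.760.
- Changed settings (Wald): one-sided alpha 1.453, 85% power 1.557, 90% power 1.609.

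**Step 6: reverse check.** For 80% power at 1.572, the conditional, Wald, log rate ratio and exact methods need about 61 to 65 comparator events, not 74. The two null-variance log formulas would need about 72 and 77, but Step 5 rules them out on the other rows.

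**The case against.** The strongest objection is that the sponsor's formula is unseen. The corrected conditional test matches the other rows closely but not to the last printed digit, and the fit within 0.01 holds at the rounded event counts. At unrounded counts the same formula gives 2.437 for liver-related deaths (13.71 events, printed 2.410) and 2.122 for myocardial infarction (20.43 events, printed 2.136). The value of 1.5274 for malignancy at 74.12 events is therefore not extra proof of 1.527. This stands, and it is why the transposition is called very probable and not certain. It does not rescue 1.572: the malignancy row remains the clear outlier, no method tried gives that value, and the conflict between table and sentence needs no formula at all.

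The second objection is that almost nothing follows from the error. The sample size came from feasibility work and consultation with regulators. The SAP states no hypotheses (4.1) and no formal stopping rules (3). The event count is right, and the printed entry errs on the cautious side by about 3% (1.572/1.528 = 1.029). All of this is true, and it limits the point to a minor correction.

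**Conclusion.** The concern holds. The table and the sentence contradict each other in both documents, and the table entry is almost certainly the wrong one. The detectable relative rate for malignancy is about 1.53. The printed 1.572 is too high by about 0.044 and corresponds to about 86% power, not 80%. The effect is to understate slightly the study's sensitivity for malignancy.

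The size of the discrepancy rests on the plan's own event count, equal person-time, and a formula inferred from its fit to the other five rows. The existence of the contradiction rests on none of these. This is a minor but clear correction.

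**What to change.** Check the malignancy figure against the original sample-size calculation, then change that entry in Table 2 of the protocol and of the SAP to 1.527. The cost is one table entry in each document; sample size, endpoints and analyses stay as they are.

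A separate query, not claimed as an error, can be settled at the same time. The SAP 4.2.1 text as supplied reads "5 per 1,000 person-years for myocardial infarction" directly after a superscript citation, where the protocol gives 3.5. A leading "3." may simply have been lost in reading the PDF, so check the original page. If 5 is really printed there, change it to 3.5, which fits the SAP's own table: 3.5 × 5.835 = 20.4 events against 20 printed. A rate of 5 would give 5 × 5.835 = 29.2 events and a detectable rate of about 1.91, not 2.136.
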